5.1 Study design

The PEARLY study is a prospective, observational, multi-center, multi-country, active surveillance registry study.

Different populations (based on different indications) will be included in the study with different subsequent analyses and separate data collection/follow-up for each of the cohorts of interest (see [Figure 1](#)). The different indication areas of interest include:

Cohort A: bleeding in early pregnancy/recurrent pregnancy loss

Cohort B: IVF/ART

A comparison of live birth rates and rate of major malformations in fetus and newborns will be based on indication area and by treatment (dydrogesterone, other progestogens, or other treatment).

[figure not shown]
Primary analyses focus on the rate of major malformations with exposure in the first trimester of pregnancy to:

- (1) Dydrogesterone versus non-dydrogesterone treatment

For the primary analysis, study participants taking any dydrogesterone preparation during the first trimester of pregnancy (at any time regardless of dosage and duration) as mono-treatment will be considered in the dydrogesterone group. Study participants taking at least one non-dydrogesterone preparation during the first trimester of pregnancy (at any time regardless of dosage and duration) as mono-treatment (i.e. no combination with dydrogesterone or another non-dydrogesterone) will be considered in the non-dydrogesterone group.

Further subgroups regarding specific dosage and duration will be considered in subgroup analyses.

Figure 1: Study Design

DYD: dydrogesterone, EDD: Estimated Date of Delivery, FU: follow-up, W: week, REOS: Regular End Of Study

5.2 Setting

The study will be conducted by the Berlin Center for Epidemiology and Health Research (ZEG Berlin), with the oversight of Abbott AG. The study will be divided into 2 phases: a baseline survey, which includes an initial consultation at baseline with recruiting Health Care Practitioners (HCPs) and completion of a baseline questionnaire by the study participant, and a follow-up phase, which includes two follow-up contacts directly with the study participant at approximately 24 weeks of gestation and 6 to 12 weeks after the initial Estimated Date of Delivery (EDD).

The study will take approximately four years and includes the recruitment and follow-up of approximately 11,000 study participants.

The study will be conducted in Russia, Turkey and China and focuses on recruiting study participants from different geographical regions, healthcare systems and cultural practices. This allows generalizability of the study results to further regions where dydrogesterone is marketed.

During study conduct, ZEG Berlin will establish two project teams – the central ZEG Berlin study team and the local Field Organizations team. The central study team is responsible for ensuring that the study adheres to the protocol and relevant rules and regulations governing non-interventional studies (NIS). The local Field Organizations team is responsible for study administration in local geographic areas, including liaising with recruiting HCPs, study participants, translation of study questionnaires, medical information, and documentation.

5.2.1 Selection of the Study Population

Study participants will be enrolled by recruiting HCPs. The recruiting HCPs are not necessarily involved in the subsequent follow-up (FU) of study participants. The recruiting HCP's role is to explain the nature of the study, its purpose and associated procedures, and the expected duration of follow-up for each study participant prior to their entry into the study.

Potential study participants will be identified by recruiting HCPs following initiation of progestogen or other treatment within the first trimester of pregnancy. Study participants will be recruited based on the inclusion and exclusion criteria as defined in section 5.2.2. Study population. As this is an observational registry study, the decision to prescribe dydrogesterone or other treatment is solely at the discretion of the HCP and the study participant. Study participants will continue to be managed throughout the study according to their HCP's prescribed treatment and will not be allocated to a study intervention.

Study participants will have the opportunity to ask questions and will be informed about their right to withdraw from the study at any time without disadvantage and without having to provide reasons for their decision. This information will be provided during the consenting process. Participation to the study is only possible if the informed consent and data privacy form is signed by the study participant. Once enrolled, a study participant may discontinue (and restart) treatment or may switch to another treatment as advised by the HCP at any time. However, study participants will continue to be followed whether or not they remain on the prescribed treatment, provided that they do not withdraw their consent.

Data will be collected directly from the study participants through electronic patient-reported outcome (ePRO) questionnaires. This means that study participants will be followed by ZEG Berlin independent of the HCP and follow-up is not necessarily linked to a clinical office visit. ZEG Berlin will obtain permission from the study participant to contact *any* treating or diagnosing HCP for clarification of a reported medical events (e.g. major malformations) during the study's observation time.

5.2.2 Study population

Subjects receiving treatment with any progestogen, including dydrogesterone, or other treatment in the first trimester of pregnancy following; (A) a diagnosis of early bleeding in pregnancy or recurrent pregnancy loss, or (B) following IVF/ART embryo transfer will be eligible to be enrolled. The inclusion and exclusion criteria are defined in section 5.2.2.1. and section 5.2.2.2.

Subjects can be screened for the study only after an informed decision for dydrogesterone or alternative treatment has been made by the subject and the recruiting HCP. Indication and contraindications according to the local market authorization/ summary of product characteristics (SmPC) should be carefully considered by the HCP.

5.2.2.1 Inclusion Criteria

- Pregnant women who wish to sustain their pregnancy
- Women who have tested positive (blood or urine) for pregnancy in the first trimester, seeking medical treatment
- Aged 18 – 35 years

AND

- Early bleeding in pregnancy with evidence of an intrauterine pregnancy / unexplained recurrent pregnancy loss (with ≥ 2 previous pregnancy losses) with evidence of an intrauterine pregnancy with visible gestational sac

OR

- Having undergone IVF/ ART embryo transfer and taking progestogen for luteal phase support (LPS), with evidence of an intrauterine pregnancy with visible gestational sac

OR

- Without taking a progestogen and advised an alternative treatment, in context of bleeding in early pregnancy, recurrent pregnancy loss, or undergoing natural cycle frozen embryo transfer (NC-FET)

AND

- Signed informed consent, allowing consent to contact all treating, or diagnosing HCP
- Able and willing to read and comprehend written instructions; comprehend and complete the questionnaires required by the protocol.

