Congenital malformations are structural abnormalities of prenatal origin and can be classified into three groups based on their cause: genetic, environmental or multifactorial (e.g., twinning) [6]. Most congenital malformations (i.e., structural birth defects) result from abnormal development during embryogenesis [7]. The present study is being designed to assess maternal and newborn safety after progestogen exposure in early pregnancy. It aims to accurately characterize the demographic profile of users of progestogens in early pregnancy including past gynecological and obstetric history, indication for progestogen use (specific focus will be given to documenting use during IVF/ART and as treatment for bleeding in early pregnancy or recurrent pregnancy loss), type of progestogen and detail of the course of pregnancy, birth outcome and newborn health. A comparison of live birth rates and rate of malformations in fetus and newborn will be based on indication area and by treatment (dydrogesterone, other progestogens, or other treatment). In keeping with regulatory requirements, reportable adverse drug reactions will be relayed to the relevant marketing authorization holders (MAHs).

4.1 Primary Objectives:

- Assess the rate of major malformations in fetus and newborns by indication and by exposure to progestogens *during the first trimester of pregnancy*, with an emphasis on dydrogesterone versus non-dydrogesterone treatments.

4.2 Secondary Objectives:

- Describe the rate of other malformations by progestogen type and indication of use,
- To describe demographic, reproductive, and maternal health data, as well as available information on prenatal diagnostics and pregnancy outcome for the mother and the newborn.

4.3 Explorative Objectives:

- Characterize the hormonal and non-hormonal utilization patterns of dydrogesterone and non-dydrogesterone treatment in study participants and describe captured background risk scenarios which may serve as causal factors for major fetal and newborn malformations, not only limited to start and stop dates for all products taken during pregnancy, but also including duration, and indication,
- Describe the rate of (spontaneous) miscarriage,
- Describe the rate of induced abortions which may be attributed to maternal health or malformations in the fetus.

5 Research methods

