5.3.2.4 Variables collected per timepoint

Variables	Baseline	FU1 At week 24	FU2 6-12 weeks after EDD
Filled by	Participant (ePRO)	Participant (ePRO)	Participant (ePRO)
Study eligibility status (based on inclusion and exclusion criteria)	Assessed by recruiting physician & via participant screening form in EDC system by study participant	NA	NA
Informed Consent	x	NA	NA
Select indication for study inclusion (cohort A or B)	x		
Demographic and social characteristics			
Body weight (in Kg) before current pregnancy	x		
Current body weight		x	x

Variables	Baseline	FU1 At week 24	FU2 6-12 weeks after EDD
Filled by	Participant (ePRO)	Participant (ePRO)	Participant (ePRO)
Height (in cm)	x		
Birth year	x		
Race	x		
Region of residence (rural, urban)	x		
Education	x		
Monthly household income	x		
Pregnancy/Reproductive History			
Week since last menstrual period	x	x (only for IVF/ART group not being pregnant at study start)	
Time to pregnancy since pregnancy wish	x	x (only for IVF/ART group not being pregnant at study start)	
Previous Pregnancy/-ies and outcome	x		
Including previous malformations	x		
Treatment			
Study treatment for indication	x	x	
Treatment start	x		
Treatment duration	x		
Fertility treatment for current pregnancy	x		
Medical History			
Existing obstetric disease & treatment	x		
Pregnancy-related/new obstetric disease & treatment		x	x
Infections during pregnancy	x	x	x
COVID-19 vaccination	x	x	x
Environmental Exposure			
Vitamin intake	x	x	
Folic acid intake	x	x	
Environmental exposure	x	x	x
Family History			
Family history malformations	x		
Personal history malformations	x		
Consanguinity	x		
Lifestyle			

Variables	Baseline	FU1 At week 24	FU2 6-12 weeks after EDD
Filled by	Participant (ePRO)	Participant (ePRO)	Participant (ePRO)
Smoking	x	x	x
Alcohol consumption	x	x	x
Study outcome parameters			
Current pregnancy status		x	x
Outcome pregnancy		x	x
Reason for end of pregnancy (if applicable)		x	x
Date of pregnancy end (if applicable)		x	x
Malformations identified in fetus/newborn		x	x
Date of diagnosed malformation (if applicable)		x	x
Diagnostic test identifying the malformation (if applicable)		x	x
Date of delivery			x
Weight newborn at birth			x
Height newborn at birth			x
Sex of the fetus/newborn		x	x

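### Women not taking a progestogen can enter on a positive pregnancy test alone, while the other entry routes require evidence of an intrauterine pregnancy; this can bias the planned live-birth comparison against the other-treatment group

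*Protocol*

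**What the plan says.** Section 5.2.2.1 first sets conditions for everyone. One is a positive test: "Women who have tested positive (blood or urine) for pregnancy in the first trimester, seeking medical treatment". Three routes joined by OR follow.

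- **Route 1, bleeding or recurrent loss:** "Early bleeding in pregnancy with evidence of an intrauterine pregnancy / unexplained recurrent pregnancy loss". For recurrent loss, at least two losses are required, "previous pregnancy losses) with evidence of an intrauterine pregnancy with visible gestational sac". This route is not limited to progestogen users.
- **Route 2, IVF/ART:** the woman must be "taking progestogen for luteal phase support (LPS), with evidence of an intrauterine pregnancy with visible gestational sac".
- **Route 3, no progestogen:** "Without taking a progestogen and advised an alternative treatment, in context of bleeding in early pregnancy, recurrent pregnancy loss", or NC-FET. No intrauterine or sac evidence is stated, and recurrent loss is not defined again.

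Sections 5.2.1, 5.2.2 and 5.2.2.2 do not restore the missing condition.

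On outcomes, section 4 states: "A comparison of live birth rates and rate of malformations in fetus and newborn will be based on indication area and by treatment". The treatment groups are dydrogesterone, other progestogens and other treatment; the Abstract and section 5.1 say much the same. Section 4.3 lists the miscarriage rate as an explorative item to be described. Section 5.7.2 takes the malformation incidence over all pregnancies observed in the cohort.

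The schedule in section 5.3.2.4 has two items at the week-24 contact marked "only for IVF/ART group not being pregnant at study start".

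**The concern.** A pregnancy must survive to the point of confirmation to enter by route 1 or 2, but not to enter by route 3. Losses between a positive test and confirmation can therefore be counted among women without a progestogen, and cannot be counted among women who had to be confirmed first. Even if treatment does nothing, the group with later entry shows more live births and fewer miscarriages.

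Cohort B is the clearest case. Route 2 demands a progestogen, so an untreated NC-FET woman can enter on the IVF/ART indication only by route 3. Every IVF/ART progestogen user needs a visible sac; no untreated NC-FET woman does. In Cohort A an untreated woman may qualify by route 1, but route 3 lets her bypass its conditions. Read literally, explained recurrent loss or fewer than two previous losses can also enter by route 3 only.

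Section 5.9 assumes that selection differences do not differ between cohorts. Here the eligibility rule can itself create one between treatment groups.

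**Working it through.** The plan gives no figure on this point, so there is nothing to reproduce. The check is a no-effect illustration of what unequal entry can do.

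**Inputs**

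- L, loss after confirmation: 10–20%. This is an assumption, anchored to the overall miscarriage risk in section 3.
- q, loss between positive test and confirmation: 2–10%. Assumed; not in the protocol.
- s, share of the comparator entering before confirmation: 25–100%. Assumed; not in the protocol. Diluting untreated women with other-progestogen users lowers s.
- Malformation risk: 2% (section 5.5), with none detected in losses before confirmation.

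**Formulas (no treatment effect)**

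- Live birth with confirmed entry: 1 − L.
- Live birth in the comparator: (1 − s)(1 − L) + s(1 − q)(1 − L) = (1 − sq)(1 − L).
- Spurious difference: sq(1 − L).
- Miscarriage ratio, confirmed entry over comparator: L / [L + sq(1 − L)].
- Malformation OR over all pregnancies: odds of 0.02 divided by odds of 0.02(1 − sq).

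**Live birth**

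- L = 10%, q = 5%, s = 100%: 90.0% against 85.5%, a difference of 4.5 points.
- L = 20%, q = 5%, s = 100%: 80.0% against 76.0%, 4.0 points.
- L = 10%, q = 5%, s = 25%: 0.25 × 0.05 × 0.90 = 1.1 points.
- Smallest in range: 0.25 × 0.02 × 0.80 = 0.4 points.
- Largest in range: 1.00 × 0.10 × 0.90 = 9.0 points.

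**Miscarriage ratio**

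- q = 5%, s = 100%: 0.10/0.145 = 0.69 at L = 10%, and 0.20/0.24 = 0.83 at L = 20%.
- Range: from 0.20/0.204 = 0.98 to 0.10/0.19 = 0.53.

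**Primary malformation OR**

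- sq = 0.005: (0.02/0.98)/(0.0199/0.9801) = 1.005.
- sq = 0.10: (0.02/0.98)/(0.018/0.982) = 1.11.

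Undetected malformations in early comparator losses lower the comparator rate, so the OR rises, against dydrogesterone.

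**After alignment.** If all routes need the same evidence, q no longer acts on one group alone. The live-birth difference is then 0 and the miscarriage ratio 1.00.

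**The case against.** Much of the case for leaving this alone is sound.

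- **No test is at stake.** Live birth is not a listed objective in sections 4.1 to 4.3, and miscarriage is only described. No margin or sample size rests on either. This stands and limits the weight of the point.
- **The primary endpoint is hardly touched.** A reader might infer that the non-inferiority result is compromised. The calculation does not support that: the shift is small against a margin of 2.0 and runs in the conservative direction.
- **The asymmetry is not universal.** A reader might infer that every progestogen user needed a visible sac and every comparator did not. For bleeding, the text clearly asks only for intrauterine evidence. Untreated Cohort A women may use route 1, and other-progestogen users face the same conditions as dydrogesterone users.
- **Enrolment may be later in practice.** Excluding multifetal pregnancy (section 5.2.2.2) is hard without a scan, and entry follows the treatment decision. Neither mandates confirmation, so the gap stays open.
- **Route 3 may be shorthand** for the recurrent-loss term defined just above it. That is plausible, but eligibility text should not depend on it.
- **The schedule entries prove little about mechanism.** They refer to the IVF/ART group as a whole, so they do not show that only comparators enter early. They remain inconsistent with criteria that require pregnancy at entry.
- **Analysis method belongs to the SAP.** A reader might infer that crude proportions ignoring entry time will be used. The protocol does not say so: weeks since last menstrual period are collected at baseline, section 5.7.1 foresees regression adjustment, and section 5.7.2 defers detail to the SAP.

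The last point does not remove the need for common eligibility. Section 5.3.2.4 lists an overall eligibility status but no separate item for sac or ultrasound confirmation, so restricting to confirmed pregnancies later may not be possible.

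**Conclusion.** The inconsistency in section 5.2.2.1 is real and should be corrected. As written, it permits a bias in live birth and miscarriage towards the progestogen groups. The bias is greatest against the other-treatment group taken alone and is diluted in the pooled non-dydrogesterone group. The criteria make it possible, not certain.

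Its size, about 0.4 to 9.0 points in live birth, rests on assumed early loss and an assumed share entering early. A single headline such as 7 points (16.0% later loss for entry at week 5 against 9.0% at week 7) can be produced. It needs an assumed weekly hazard of 0.045 × exp(−0.30 × (week − 5)) over weeks 5 to 19, with one whole group entering at week 5 and the other at week 7. The protocol gives no entry week for any group and no week for sac visibility, so the range is the fair statement. The effect on the primary malformation OR is about 1.005 to 1.11, against dydrogesterone.

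**What to change.** In section 5.2.2.1, attach to the third route the evidence already used for the matching indication: intrauterine evidence for bleeding, and an intrauterine pregnancy with visible sac for recurrent loss and for NC-FET. Carry over the same recurrent-loss definition (unexplained, at least two losses). If the visible-sac condition is also meant to cover bleeding in route 1, say so there and mirror it in the third route.

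In section 5.3.2.4, reconcile the two entries for IVF/ART women not pregnant at study start with inclusion criteria that require pregnancy at entry.

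The cost is a short eligibility amendment and a schedule correction. Some untreated women will enrol slightly later or not at all.

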This multinational, prospective, active surveillance, registry study following two cohorts will include study participants who are pregnant and seeking any type of medical*** treatment, including dydrogesterone and other progestogens, for either (A) recurrent pregnancy loss* and/or bleeding in early pregnancy** or (B) as IVF/ART support. Pregnant women not taking progestogen and are advised an alternative non-medical treatment, in the context of bleeding in early pregnancy, recurrent pregnancy loss, or undergoing natural cycle frozen embryo transfer (NC-FET) can also be included in this study. Eligible study participants will be recruited via an international network of prescribing Health Care Practitioners (HCPs) in China, Turkey, and Russia with the aim to collect data related to maternal safety and newborn safety in women prescribed progestogens during early pregnancy. Study participants will be followed from early pregnancy until 6 – 12 weeks after giving birth. All malformations will be captured via direct contacts with the study participants. Study participants will be sent online questionnaires via the electronic Patient Reported Outcomes (ePRO) solution provided by MediData. Major malformations reported by the study participants will be validated by ZEG Berlin via relevant source documents and if necessary, via contacting the treating HCPs. The total study duration is planned for approximately 4 years including recruitment and follow-up.

Population

Pregnant women aged 18 to 35 who are treated with progestogens, including dydrogesterone, or other treatment for (A) recurrent pregnancy loss* and/or bleeding in early pregnancy** or as (B) IVF/ART support can be included in the study. Study participants are only recruited after the decision on treatment is made. Additionally, study participants will be recruited in different geographical areas in China, Turkey and Russia where dydrogesterone is marketed.

*habitual miscarriage / ** threatened miscarriage

*** Other treatments contain medical i.e., non-drug treatment plan (e.g. yoga, meditation, bed rest), pharmaceutical i.e., prescribed non-dydrogesterone based drug therapy including over-the-counter (OTC) and medicinal i.e., non-pharmaceutical including herbal, traditional medicines etc.

Variables

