5.9 Limitations of the research methods

The general limitations of observational research and the particularities of the non-interventional/registry approach remain valid. In non-experimental studies the possibility of bias and residual confounding can never

be entirely eliminated, and the ability to infer causation is correspondingly limited. As modern epidemiology has evolved, improved insight into potential sources of bias and confounding, as well as refinements of statistical and epidemiologic methodology, help the epidemiologist to estimate the impact of potential bias and residual confounding.

The design of this study pays particular attention to the following typical biases:

- Confounding bias: subject characteristics (i.e., demographics, socioeconomic factors) that influence the outcome might have unbalanced distributions across treatment groups. Potential differences in outcome could be caused by these differences. Several statistical approaches (i.e., multivariable regressions and propensity score analysis) are planned to balance the distribution of characteristics between treatment groups, reducing the chance of confounding bias, and therefore allowing plausible estimates of the association of dydrogesterone use and major malformations.
- Channeling bias: non-random assignment of subjects to treatment can lead to imbalances in risk-factors between the groups being compared and thus bias the estimates of the treatment effect. Various statistical techniques such as propensity score analyses will be considered.
- External validity: if multiple countries are involved, country specific healthcare settings may play a role with regard to the selection of study participants. With the approach used in the PEARLY study, representativeness will be improved by including the participation of obstetric practitioners, as well as clinics and family planning centers, etc., leading to a representative mix of the typical institutions prescribing dydrogesterone.

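### In cohort B, women without a progestogen can enter only after NC-FET, so comparing them with progestogen users over the whole cohort mixes treatment with transfer type

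*Protocol*

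**What the plan says.** **Who may enter cohort B.** Protocol section 5.2.2.1 gives progestogen users a route with no limit on transfer type: "Having undergone IVF/ ART embryo transfer and taking progestogen for luteal phase support (LPS". Women without a progestogen have a separate route, whose permitted contexts are early bleeding, "recurrent pregnancy loss, or undergoing natural cycle frozen embryo transfer (NC-FET". The first two are cohort A indications, so NC-FET is the only IVF/ART context named. The abstract (Study design) applies the same three contexts to "Pregnant women not taking progestogen and are advised an alternative non-medical treatment". Section 5.2.2 is looser: it lists other treatment alongside progestogens and ends with "B) following IVF/ART embryo transfer will be eligible to be enrolled", but refers to 5.2.2.1 for the criteria.

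**What is compared.** Section 5.1 plans comparisons of live birth and major malformation "based on indication area and by treatment (dydrogesterone, other progestogens, or other treatment"; the abstract and section 4 say the same. The primary contrast is "1) Dydrogesterone versus non-dydrogesterone treatment". Its reference group, in section 5.7.2, pools other progestogens with other or no treatment.

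**How confounding is handled.** Section 5.7.2 offers propensity-score methods such as IPTW, or covariates in the logistic model. On channeling, section 5.9 says only: "Various statistical techniques such as propensity score analyses will be considered". Section 5.3.2.3 names IVF/ART insertion technique as an example of a variable to be collected and points to 5.3.2.4 for the full list. That grid has no row for transfer type. The nearest item is the baseline entry on fertility treatment for the current pregnancy.

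**The concern.** The eligibility rule ties one treatment category to one transfer type. In cohort B the other treatment group is all NC-FET, while the two progestogen groups may be any mixture of fresh, natural-cycle frozen and other frozen transfers. Any difference in live birth or malformation risk between NC-FET and other transfers then appears as a treatment difference.

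The planned methods assume that each kind of woman could have been in either group. Outside NC-FET the probability of being a non-progestogen participant is zero by eligibility. Inverse-probability weights for that group do not exist there, and a regression coefficient is carried over from NC-FET by model assumption alone. Section 5.9 treats channeling in general terms and does not mention this restriction.

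Data capture is also at stake. If transfer type is not recorded at baseline, no later analysis plan can restrict to NC-FET or adjust for it.

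**Working it through.** **1. Overlap by transfer type, read from section 5.2.2.1**

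| Cohort B transfer type | Dydrogesterone | Other progestogen | No progestogen |
|---|---|---|---|
| NC-FET | admitted | admitted | admitted |
| Any other transfer | admitted | admitted | no route named |

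- Dydrogesterone vs other progestogens: same entry rule, no structural gap.
- Either progestogen group vs other treatment: overlap in the NC-FET row only.
- Dydrogesterone vs pooled non-dydrogesterone: overlap in both rows, because other progestogens supply the second.

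**2. Size of the unadjusted distortion.** The protocol gives no figure on this point. Table 2 concerns the pooled contrast and is not in question. From the protocol comes a 2% malformation risk. Assumed, with ranges:

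- NC-FET risk ratio R against other transfers: 0.7 to 1.25
- share s of progestogen users with NC-FET, equal in both progestogen groups: 0 to 0.3
- share f of the pooled reference without a progestogen: 0.05 to 0.5
- true treatment odds ratio: 1

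Formulas:

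- progestogen risk: p_D = 0.02 × (1 − s + sR)
- other treatment risk: p_O = 0.02 × R
- pooled reference risk: p_P = (1 − f) p_D + f p_O
- crude OR = odds(p_D) / odds(p_O), or odds(p_D) / odds(p_P)

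Dydrogesterone vs other treatment:

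- s = 0, R = 0.7: (0.02/0.98) / (0.014/0.986) = 1.44
- s = 0, R = 1.25: (0.02/0.98) / (0.025/0.975) = 0.80
- s = 0.3, R = 0.7: p_D = 0.02 × 0.91 = 0.0182; (0.0182/0.9818) / (0.014/0.986) = 1.31
- s = 0.3, R = 1.25: p_D = 0.02 × 1.075 = 0.0215; (0.0215/0.9785) / (0.025/0.975) = 0.86

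Dydrogesterone vs pooled reference, s = 0:

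| f | R = 0.7 | R = 1.25 |
|---|---|---|
| 0.05 | 1.02 | 0.99 |
| 0.20 | 1.07 | 0.95 |
| 0.50 | 1.18 | 0.89 |

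Example: f = 0.5, R = 0.7 gives p_P = 0.017 and (0.02/0.98) / (0.017/0.983) = 1.18.

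Dydrogesterone vs other progestogens: 1.00 when their transfer mix is the same.

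For live birth, if other transfers differ from NC-FET by d percentage points, the crude difference against other treatment is shifted by (1 − s) × d.

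**3. Consequence for the primary test.** Unadjusted one-sided score test of OR = 2.0, simulated with 5,500/2 × 0.8 = 2,200 per group and 2% risk in other transfers. The false-positive rate uses a true OR of 2.0 and an NC-FET baseline OR of 1.25; power uses a true OR of 1 and a baseline OR of 0.8.

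| NC-FET share, dydrogesterone / reference | False-positive rate | Power |
|---|---|---|
| 0% / 0% | 2.6% | 89% |
| 0% / 5% | 3.1% | 88% |
| 0% / 25% | about 5.4% | 83% |
| 25% / 25% | 2.6 to 2.7% | 88% |

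The imbalance in NC-FET share drives the result. The protocol states no such share.

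**The case against.** **Overlap exists.** A reader might infer that treatment and transfer type are fully confounded in cohort B. The documents do not support that. Section 5.2.2.1 lets progestogen users enter after NC-FET, so a comparison within NC-FET is possible. Confounding would be complete only if no progestogen user had NC-FET, which the protocol does not say. This objection stands, and the fix depends on it.

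**The affected contrast is not the powered one.** Section 5.7.2 attaches the non-inferiority hypothesis to the pooled comparison and treats subcohorts of the reference as secondary or sensitivity analyses. No hypothesis is attached to live birth. A reader might apply the margin of 2.0 to the direct contrast. With 550 NC-FET women (25% of 2,200), the assumptions of step 3 and no adjustment, false non-inferiority is about 13% instead of 3.1%, and power 27% instead of 52%. Those figures are a worst case with no NC-FET among dydrogesterone users, for a test the protocol does not plan.

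**The remedy is partly there.** Insertion technique is named as a variable, and covariate adjustment is planned. For the pooled contrast this suffices if the variable distinguishes transfer types. A propensity model that included transfer type and was trimmed to the region of overlap would reach the same restriction. Such modelling detail may properly sit in the SAP. What remains is that insertion technique is not defined as transfer type, that the grid meant to list all variables has no such row, and that the conflict between the eligibility rule and the planned comparison lies in the protocol itself.

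**The rule is not watertight.** Section 5.2.2 is broader, and a non-progestogen woman who bleeds after another kind of transfer might enter through the bleeding context, with her cohort unclear. That is a reason to clarify the text; it does not supply a planned comparator outside NC-FET.

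**Conclusion.** The point holds for two of the three pairwise contrasts in cohort B: dydrogesterone versus other treatment, and other progestogens versus other treatment. Over the whole cohort neither can be separated from transfer type without extrapolation. Under the stated assumptions, a true odds ratio of 1 for malformation would appear, unadjusted, between 0.80 and 1.44. The direction is unknown because the protocol gives no risk by transfer type.

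Dydrogesterone versus other progestogens is not affected by the entry rule. The pooled primary odds ratio is touched only in diluted form: 0.99 to 1.02 if 5% of the reference is non-progestogen, 0.89 to 1.18 at 50%. There is no distortion when NC-FET shares match, and ordinary adjustment can handle the rest. A reader might infer that the primary conclusion is compromised; the protocol does not support that.

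This is worth correcting because it determines what the comparison with non-progestogen women can show, and because transfer type that is not collected cannot be recovered later.

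**What to change.** - In sections 5.1 and 5.7.2, state that cohort B contrasts with non-progestogen women are restricted to NC-FET women in every treatment group.
- Add transfer type (fresh, NC-FET, other frozen) explicitly to the grid in section 5.3.2.4, for example as an answer option under the existing baseline item on fertility treatment.
- Include transfer type as a covariate in the pooled cohort B model. Dydrogesterone versus other progestogens can stay across all transfer types.
- Reconcile section 5.2.2 with 5.2.2.1, and say to which cohort a non-progestogen woman with bleeding after another type of transfer belongs.

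The cost is protocol or SAP wording and one answer option; treatment, eligibility and sample size do not change. The restricted contrast loses precision. With 2% risk, SE(log OR) = √[(1/(0.02 × 0.98)) × (1/n_D + 1/n_O)]. Assuming 550 non-progestogen women, using all 2,200 dydrogesterone users gives 0.34. If 20% of them (440) had NC-FET, it gives 0.46. If few progestogen users have NC-FET, the contrast can only be descriptive, and the report should say so.
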